## **A. BACKGROUND**

Obstructive sleep apnea (OSA) is characterized by repetitive interruption of ventilation during sleep due to collapse of the pharyngeal airway. A diagnosis of OSA is established when a patient has an apnea-hypopnea index (AHI)  $>5$  and symptoms of excessive daytime sleepiness. OSA affects an estimated 15 million adults and is prevalent in a large percentage of patients with hypertension and other forms of cardiovascular disease. Obesity and male sex are recognized risk factors for the presence of sleep-disordered breathing.

OSA is a recognized risk factor for ischemic stroke. The mechanisms whereby OSA increases the risk of stroke are complex, including hypoxia, increased likelihood of arrhythmia and congestive heart failure, increased atherosclerosis, and production of inflammatory changes in the blood. Although OSA is well recognized as an independent stroke risk factor, little focus has been devoted to modifying potential stroke risk factors in patients with OSA.

One of the mechanisms whereby OSA can lead to ischemic stroke is via atrial fibrillation (AF). AF is the leading cause of cardioembolic stroke and there is an important bidirectional relationship between these two conditions. OSA is present in up to 50% of patients with AF. Also, when patients with OSA are followed longitudinally, up to 15% will develop AF over a five year period.

In addition to overt AF, performance of the polysomnogram (PSG) will allow the detection of premature atrial contractions (PACs). PACs are a recognized potential predictor for AF.

Early detection of AF in patients with OSA is important since oral anticoagulants are extremely effective for stroke prevention in patients with nonvalvular AF. Institution of anticoagulation in the patient population with coexistent AF and OSA represents a significant opportunity for primary stroke prevention.

## **B. METHODS**

The specific goal of this study is to assess the frequency of AF in patients with OSA using a cardiac event monitor ([www.lifewatch.com](http://www.lifewatch.com)). We will specifically target OSA patients with a CHADS score of  $\ge 2$ .

Patients who are newly diagnosed with OSA (within the last 12 months) based on a PSG at one of our participating hospitals will be eligible. Patients with a CHADS score of  $\ge 2$  will be approached for evaluation with a two week cardiac event monitor. The target sample size is 200 patients. The rationale for this sample size is provided below.

### **Inclusion and Exclusion Criteria**

#### **Inclusion Criteria**

1. Diagnosis of OSA within the last 12 months
2. No previous diagnosis of atrial fibrillation

3. Able and willing to follow-up as an outpatient

4. Age 40-85 years

**Exclusion criteria**

1. Life expectancy < 2 years

2. Dementia or other neurologic condition which would make outpatient follow-up difficult

3. CHADS score <2

4. Alcohol or drug abuse which would interfere with outpatient follow-up

5. Severe CHF (NYHA class 3 or 4) or use of LVAD

6. Current dialysis treatment or planned treatment within 12 months

7. Known bleeding disorder or prothrombin time >15 seconds

8. Mechanical heart valve requiring anticoagulation

9. Moderate to severe mitral stenosis or regurgitation

10. Prior clinical diagnosis of ischemic stroke (radiologic infarcts are not excluded)

11. COPD with oxygen dependence

12. Pregnant patients or patients that plan to become pregnant within the course of the study\*.

13. Patients with anticipated need for a pacemaker during the course of the study

\*If any patients become pregnant during the course of the study, pregnancy outcomes will not be followed

**Treatment Plan and Dosing Regimen**

Patients will be screened for atrial fibrillation with the Lifewatch ACT MCT monitor. If positive for AF, results will be provided to the patient's primary care physician and outpatient antithrombotic medication use in the following six months will be recorded. The Lifewatch interpretation will be sent by FAX to the patient's primary care physician for patients recruited at the University of Miami Sleep Center.

Cardiology consultation will be encouraged for patients with newly detected AF.

**Subject Recruitment**

The study coordinator will work with the PI and co-investigators to institute screening procedures for eligible subjects at the two sites, also, protected health information will be access prior as well during

the course of the proposed research. All newly diagnosed OSA patients who meet the study criteria will be invited to join the study. In addition, patients with a diagnosis of OSA within the previous 12 months will also be asked to participate if they meet all the study criteria. Patients who will be approached for participation in the study are already under the care of the sleep physicians who are co-investigators in the study.

Prior to study initiation, an educational presentation will be provided to the Sleep Program personnel (including staff physicians, fellows) to review the nature and purpose of the study. The physicians involved in the Sleep Program have regular conferences in which the study will be highlighted. The PI will work with the study coordinator and co-investigators to review study enrollment on a biweekly basis. Any obstacles to enrollment will be addressed by the study staff.

A summary of the study schedule of events is provided in Appendix one.

#### **Description of cardiac monitoring device**

The Lifestar ACT MCT monitor is a continuous ECG monitor and arrhythmia detector that is designed for self-testing by patients at home and for analysis by medical professionals at a remote Monitoring Center. The chest-worn sensor is utilized for the acquisition, recording, and transmission of the ECG signal. The device is equipped with four electrodes on a harness and it houses a 3.6V AA battery, a Bluetooth transceiver and a buzzer. Patients will be monitored over a 2 week of period.

The ECG signals are transmitted via Bluetooth to a handheld device with a proprietary interactive application, arranged to process and transmit the ECG recordings. The handheld device is mobile computing device with a display and a touch input such as a cell phone. It has adequate memory and processing capability to run the proprietary application. This device is already used for routine clinical care at both the University of Miami Hospital and the Miami VA Hospital. A patient quick start guide is attached as an appendix.

#### **Outcome Measures**

After completion of the four week cardiac event monitor, we will record the frequency of abnormalities such as:

1. Frequent premature atrial contractions
2. Frequent ventricular premature contractions
3. Definite AF (defined as an irregularly irregular rhythm with absence of p waves)
4. Longest duration of AF
5. AF episodes lasting more than six minutes

Initial interpretation of the cardiac monitor is provided by Lifewatch technicians and the reports will be confirmed by the study assigned cardiologist. The Lifewatch technicians receive ECG information only and no identifiable information. We will follow patients for six months after the placement of the cardiac event monitor. We will document selection of antithrombotic therapy including the following:

1. Novel oral anticoagulant (NOAC)
2. Warfarin
3. Antiplatelet therapy
4. No antithrombotic therapy

After all patients have completed the six month follow-up period, we will record the following:

1. Frequency of undetected AF
2. AF frequency according to baseline CHADS score
3. Rate of utilization of anticoagulants in patients with AF
4. Rate of utilization of antiplatelet therapy in patients with AF
5. Predictors of AF based on baseline variables (age, sex, history of CHF, BMI, etc.)

If we find that >5% of patients with OSA and CHADS score of  $\geq 2$  have undetected AF, then this would support a larger multi-center study of screening OSA patients for AF and identifying predictors of AF in this population.

#### *Risk/benefit considerations*

No benefit can be guaranteed to study participants. However, if they do have early detection of AF, they can be placed on appropriate antithrombotic treatment to prevent stroke, which is a potential benefit.

There are no major risks with the device. Some patients may have skin irritation and special "sensitive skin" leads are available for these patients. There is no restriction with the use of the device with pacemakers or other implanted devices since only surface recordings are made.

### **C. SAMPLE SIZE CONSIDERATIONS**

The frequency of AF in the general population is likely to be <1%. Our hypothesis is that 5% of OSA patients screened with a four week monitor will have AF.

If  $p$  = the percent of patients with sleep apnea who have afib, then the z-test will assess the following hypotheses:

$H_0: p \leq 1\%$

$H_1: p > 1\%$

If the true value of  $p$  is 5%, then a study with 200 patients has power = 97%. That is, the probability is 0.97 that the null hypothesis ( $H_0$ ) will be rejected at a significance level of 5% in favor of the alternate hypothesis ( $H_1$ ).

The sample size needed for 80% power is 59 patients. The higher sample size is justified since the point estimate of AF frequency will be more precise with the larger sample size. Further, analysis of the predictors of AF according to baseline variables will be more fruitful with a larger sample size.

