## **J. Future Directions**

In order to have the greatest impact on stroke prevention, it is important to have AF patients on the most effective antithrombotic medication. Furthermore, it is important to have the anticoagulant medication started before a stroke to avoid permanent neurologic injury. Screening high risk patients for AF is one method to identify AF patients prior to the development of a disabling stroke.

We feel that the group of patients with OSA represents an excellent target population for AF screening due to their high frequency of multiple stroke risk factors (hypertension, diabetes mellitus, obesity, etc.). If we are able to establish that the frequency of AF in this population is at least 5%, then a larger study can be justified. Screening of OSA patients would also be a novel method for early identification of individual patients at elevated risk for ischemic stroke. Future studies could also investigate genetic polymorphisms which are associated with an increased propensity for AF. By combining genetic predisposition with environmental factors and conventional risk factors, an “AF prediction” score could be developed for patients with OSA and other conditions such as congestive heart failure.

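### The Section C test of p ≤ 1% uses a general-population benchmark for a selected, monitored sample, and does not bear on the plan's own 5% criterion

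*Combined protocol and SAP*

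**What the plan says.** Section C gives one formal hypothesis. Its benchmark is "The frequency of AF in the general population is likely to be <1" per cent, with no source, age range or method of detection. The parameter is "the percent of patients with sleep apnea who have afib, then the z-test will assess the following hypotheses": H0 is p ≤ 1% and H1 is p > 1%. The expected rate is stated as "Our hypothesis is that 5% of OSA patients screened with a four week monitor will have AF". Section C concludes that "a study with 200 patients has power = 97" per cent at a 5% significance level.

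The sample is narrower than that parameter. Section B says "We will specifically target OSA patients with a CHADS 2 score of" 2 or more, and the exclusion criteria remove lower scores. The inclusion criteria require age 40-85 and "No previous diagnosis of atrial fibrillation". All patients wear a continuous ECG monitor, for two weeks in Section B and the device description, and for four weeks in Outcome Measures and Section C. There is no group without OSA.

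The criterion for going on to a larger study is separate from the test. Outcome Measures asks for undetected AF in more than 5% of OSA patients with CHADS2 of at least 2. Section J asks for a frequency of at least 5%, and describes the target without the CHADS2 restriction: "We feel that the group of patients with OSA represents an excellent target population for AF screening".

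**The concern.** The benchmark and the sample differ in more than OSA. Selection on CHADS2, the age range and weeks of continuous recording would all tend to raise the AF found relative to a general-population figure. Excluding known AF lowers it. With no comparison group, the test cannot separate OSA from these differences. Because known AF and low CHADS2 scores are excluded, the sample also cannot estimate p as Section C words it.

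The second problem needs no assumption about background rates. The formal test and the decision criterion ask different questions of the same 200 patients. A reader who sees 97% power may take it as the chance that the study succeeds on its own terms, when it is the chance of clearing a much lower bar. A result can reject H0 and still fail the criterion for a larger study.

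**Working it through.** **Inputs.** From Section C: n = 200, null value 1%, hypothesised rate 5%, one-sided alternative, significance level 5% (z = 1.645). From Outcome Measures: criterion above 5%. From Section J: criterion at least 5%.

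**1. The plan's own power figure.** One-sample z-test, with null variance in the critical value and alternative variance in the power:

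Φ{[√200 × (0.05 − 0.01) − 1.645 × √(0.01 × 0.99)] / √(0.05 × 0.95)} = Φ{(0.5657 − 0.1637) / 0.2179} = Φ(1.84) = 96.7%.

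This reproduces the stated 97%.

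**2. Where the test rejects.** Under p = 1% the expected count is 2, with standard deviation √(200 × 0.01 × 0.99) = 1.407.
- 4 cases: z = (4 − 2)/1.407 = 1.42, not rejected.
- 5 cases: z = (5 − 2)/1.407 = 2.13, rejected.

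The test is positive from 5/200 = 2.5%. The exact (Clopper-Pearson) 95% CI at 5/200 is 0.8% to 5.7%, which still contains 1%. The two are not strictly in conflict, since the interval is two-sided and exact and the test is one-sided and approximate. Exact binomial power of this rule at 5% is P(X ≥ 5) = 97.4%.

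**3. Where the decision criterion is met.** 10/200 is exactly 5.0%, so more than 5% needs 11 cases (5.5%) and at least 5% needs 10.

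| Rule | Cases needed of 200 | Probability if true rate is 5% (exact binomial) |
|---|---|---|
| Test of p ≤ 1% | 5 | 97.4% |
| Section J, at least 5% | 10 | 54.5% |
| Outcome Measures, more than 5% | 11 | 41.7% |

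At the plan's hypothesised rate, the chance of rejecting H0 while failing the Outcome Measures criterion (5 to 10 cases) is 97.4% − 41.7% = 55.7%. Ten cases fail Outcome Measures but satisfy Section J.

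**4. What rejection says about OSA.** The documents give no rate for comparable monitored patients without OSA, so these rates are assumed for illustration. If OSA added nothing, the exact probability of rejecting p ≤ 1% would be:

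| Assumed background rate | P(X ≥ 5) |
|---|---|
| 1% | 5.2% |
| 2% | 37.1% |
| 3% | 71.9% |
| 4% | 90.5% |

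The nominal 5% error rate protects against the 1% figure only. The table shows how sensitive the test is to the benchmark; it does not show that the true background exceeds 1%.

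**5. Precision around the criterion.** The exact 95% CI at 11/200 is 2.8% to 9.6%. The lower limit first passes 5% at 17/200 (8.5%), where it is 5.03%; at 16/200 it is 4.6%. Whether the criterion applies to the point estimate or to the lower limit therefore matters a great deal.

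**The case against.** A reader might infer that the protocol sets out to show excess AF due to OSA and that the design fails at this. The documents do not support that reading. Section B gives the aim as assessing frequency, and a single-arm study of screening yield needs no group without OSA, because yield matters whatever its cause. Section J rests its choice of target on the patients' burden of other stroke risk factors, and makes a larger study depend on 5%, not on rejecting 1%. This objection stands. What remains is that Section C draws its only formal null from the general population, so a comparison is implied even though no conclusion is drawn from it.

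A reader might also infer that selection and monitoring make the test too easy to pass. That does not follow either. Excluding known AF works in the opposite direction, and the documents do not allow the net effect to be worked out. Every illustrative rate above 1% is an assumption.

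It is also fair to say that the intended quantity can be recovered from Outcome Measures, which names undetected AF and the CHADS2 restriction, and that the 97% is right for the hypothesis as written. Both stand. They make this a matter of aligning Section C with the rest of the plan. They do not remove the gap between 97% and 42%, which follows from the plan's own numbers.

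**Conclusion.** The point holds as one of definition and interpretation. Section C names a parameter that the sample cannot estimate and tests it against a benchmark that differs from the sample in several respects besides OSA. Rejecting p ≤ 1% would show only that newly detected AF exceeds 1% in this selected, monitored group. Data collection and the frequency estimate are not affected.

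The firm size is the difference between the test and the decision rule: 97% against 42%, or 55% under Section J's wording. It rests only on n = 200, the hypothesised 5% and binomial sampling. It ignores the expected dropout of under 2%, and takes 5% as the rate actually detected by the study monitor over whichever monitoring period applies.

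**What to change.** - **Section C, parameter.** Define p as the proportion of OSA patients with CHADS2 of at least 2 and no known AF in whom the study monitor newly detects AF. The monitoring period belongs in this definition, so the two-week and four-week passages must be reconciled.
- **Section C, primary result.** Make the point estimate of p with its exact 95% CI primary. Apply the 5% criterion to the point estimate, as Outcome Measures does, and report the CI as its uncertainty (2.8% to 9.6% at 11/200). Say so explicitly, because a rule on the lower limit would need 17/200.
- **Outcome Measures and Section J, criterion.** Use one wording, either more than 5% or at least 5%. The result at 10/200 turns on it.
- **Section C, test.** Label the test against 1% descriptive. State that rejecting it is not evidence that OSA raises AF frequency, and that the 97% power refers to that test alone. Give the chance of meeting the 5% criterion beside it.
- **Section J, conclusion.** Limit it to OSA patients with CHADS2 of at least 2.

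The cost is rewording, with no added patients or procedures. The downside is a narrower claim and less favourable stated operating characteristics.

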## APPENDIX ONE

Visit schedule and tasks for completion

Time	Tasks for completion
Baseline evaluation	

• CHADS score calculation*

• Obtain informed consent

• Arrange cardiac monitor for patient

• Explain plan for outpatient follow-up

• Complete baseline data collection form

• Heart monitor will be placed

1 week	

• Contact subject to verify that they are wearing the cardiac monitor.

• Ask subject about any adverse events.

• Remind subject to return the heart monitor (in person or via USPS or UPS)

• Schedule 6-month phone call follow-up. This phone call will serve as the study close-out visit.

6 months	Contact subject for study close-out visit

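### The monitor is worn for two weeks in the methods and device text but four weeks in the outcome and sample size text, and the 5% behind the 97% power is a four-week rate

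*Combined protocol and SAP*

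**What the plan says.** Two places give two weeks. In B. Methods, patients with a qualifying CHADS2 score "will be approached for evaluation with a two week cardiac event monitor". The device description says "Patients will be monitored over a 2 week of period".

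Two places give four weeks. Outcome Measures opens with "After completion of the four week cardiac event monitor, we will record the frequency of abnormalities such as". C. Sample Size Considerations states "Our hypothesis is that 5% of OSA patients screened with a four week monitor will have AF". The same section tests a null rate of at most 1% against a higher rate with a z-test at the 5% level, and gives 97% power with 200 patients if the true rate is 5%.

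The 5% figure returns as the condition for further work. Outcome Measures has "If we find that >5% of patients with OSA" and a CHADS2 score of 2 or more have undetected AF. J. Future Directions has "the frequency of AF in this population is at least 5%, then a larger study can be justified". Neither statement names a monitoring window.

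Appendix One gives no duration. Its only contact between baseline and six months is at week 1, when staff check that the monitor is being worn and remind the patient to return it.

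**The concern.** This is a single-arm study whose stated goal is to measure how often AF is found with this monitor. Time on the monitor is part of the definition of that proportion: AF seen by the end of week 2 is a subset of AF seen by the end of week 4. Until the duration is settled, the main quantity is defined only to within a factor of two in observation time, and staff working from different sections could deliver different exposures.

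The conflict also reaches the planning figures. If patients wear the device for two weeks, the planning rate, the power and the chance of passing 5% were all stated for a longer exposure than patients receive, and each can only stay the same or fall. A result at or below 5% might then partly reflect the shorter window and wrongly discourage the larger study. If patients wear it for four weeks, the power figure stands and the error is confined to the two-week statements and the timing of the return reminder.

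**Working it through.** **Inputs from C. Sample Size Considerations:** n = 200, p0 = 1%, p1 = 5%, one-sided test at 5% (z = 1.645).

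**1. Reproduce the stated power.**

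Standard error under the null: √(0.01 × 0.99 / 200) = 0.00704.

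Critical proportion: 0.01 + 1.645 × 0.00704 = 0.02157, or 4.31 patients of 200. The test therefore rejects at 5 or more AF cases.

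Standard error at 5%: √(0.05 × 0.95 / 200) = 0.01541.

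Normal power: Φ((0.05 − 0.02157) / 0.01541) = Φ(1.845) = 96.7%.

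Exact binomial power: P(X ≥ 5 | n = 200, p = 0.05) = 97.4%.

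Both agree with the stated 97%, so there is no arithmetic error.

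**2. Choose two-week rates.** The document gives no two-week rate and no ratio of two-week to four-week yield. The following are assumptions:

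- two weeks captures 90% of the four-week yield: 0.90 × 5% = 4.5%
- two weeks captures 75%: 0.75 × 5% = 3.75%
- constant hazard of first detection: 1 − 0.95^0.5 = 2.53%, about half. This is a pessimistic bound, because persistent or frequent AF is found early.

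**3. Recalculate at N = 200.** More than 5% means 11 or more of 200. At least 5%, the wording in J. Future Directions, means 10 or more.

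| True rate in the window delivered | Exact power, P(X ≥ 5) | Normal power | P(X ≥ 11), more than 5% | P(X ≥ 10), at least 5% |
|---|---|---|---|---|
| 5% (as planned) | 97.4% | 96.7% | 41.7% | 54.5% |
| 4.5% | 94.9% | 94.5% | 29.1% | 41.3% |
| 3.75% | 87.3% | 88.2% | 13.4% | 22.0% |
| 2.53% | 57.3% | 63.2% | 1.4% | 3.2% |

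**4. Find where power reaches 80%.** Exact power is 80% at a true rate of 3.34%; normal power is 80% at 3.21%. Since 3.34 / 5 = 0.67, the test against 1% tolerates the loss of about a third of the planned yield.

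**5. Separate the two effects on the 5% criterion.** Even with no loss of yield, the chance of observing more than 5% is only 42% (55% for at least 5%), because the threshold equals the planning rate. That is a different issue. Only the falls from those starting values are due to the window.

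**The case against.** The strongest reply accepts the conflict in wording and disputes its consequences.

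- **The power statement is conditional.** The sample size section defines p without a window and gives the power for a true value of 5%, which is correct at any duration. The 5% has no cited source, so it may be a round figure with an outdated duration attached. This stands in part: the effect on power is illustrative. But the only sentence that says what the 5% refers to says a four-week monitor, and a reader has to take it as written.
- **The test is robust.** It keeps 80% power down to about 3.3%. The section also says 59 patients would give 80% power and justifies 200 by precision and the analysis of predictors, so nothing shows that N would change. This stands for the test against 1%, but it does not protect the 5% criterion.
- **The 5% criterion is informal and names no window.** Its link to four weeks is inferred from the section it sits in and the shared figure. A yield of 5% or less at two weeks would be a valid answer about two-week screening. This also stands, and it is why the criterion needs a stated window.
- **Two weeks looks like the intended duration.** The recruitment and device text say so, and a return reminder at week 1 fits two weeks better. That is probable but not settled. Section E refers to a Table 1 that does not appear under that label in the text reviewed. It may be Appendix One, which gives no duration.

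These points limit how much weight the power figures should carry. None of them resolves the contradiction.

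**Conclusion.** The concern holds. Two sections state two weeks, two state four, and no visible text or amendment log reconciles them. Because duration of wear defines the AF proportion the study exists to estimate, this should be corrected as an error in the plan and not passed over as a slip of wording.

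The contradiction itself is certain. Its numerical effect is conditional: it arises only if two weeks is delivered, only if the 5% is read as a four-week rate, and its size depends on assumed capture ratios. For capture between 75% and 90%, the loss of power is modest, and it becomes serious only near the pessimistic bound. The 5% criterion is more exposed: at 75% capture, the chance of exceeding it falls by about two-thirds (from 42% to 13%).

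**What to change.** State one monitoring duration in B. Methods, the device description, Outcome Measures and C. Sample Size Considerations, and align the wear check and return reminder in Appendix One with it.

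- **If two weeks:** correct Outcome Measures and the sample size section. Restate the hypothesised AF rate for a two-week monitor and give its basis. Report the power at N = 200 for that rate and the probability of exceeding 5%. State in Outcome Measures and J. Future Directions that the 5% criterion refers to two weeks of monitoring.
- **If four weeks:** correct B. Methods and the device description, move the return reminder later than week 1, and state that the 5% criterion refers to four weeks. The 97% then needs no change.

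The cost is wording and, for two weeks, one recalculation; no additional patients are needed. The drawback of two weeks is that the stated power may become less favourable. The drawback of four weeks is that each patient wears the device for twice as long as the methods and device sections describe.

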#### **F. Data Management Plan**

The Department of Neurology at the University of Miami Miller School of Medicine has a full time statistician and has served as the clinical coordinating center for previous multi-center trials. The research infrastructure is excellent. The Neurology Department participates in two major NIH-sponsored clinical trial consortia, the NeuroNext Initiative and the Stroke Trials Network (StrokeNet).

With regard to data collection and adequacy, data will be obtained directly from the study participants via office visits or through phone follow-up, and thus we feel that the data source for those elements will be quite accurate. The electronic medical record (EMR) at the two facilities will be another source for obtaining information on any medical encounters for cardiac issues such as atrial fibrillation. Electronic case report forms will be created for data collection in the study.

Although all measures will be undertaken to prevent missing data, it is likely that there will be some missing data elements due to patients who drop out of the study. Due to the relatively short duration of study participation and the patient stipend being offered, we expect a dropout rate of <2%. To handle missing data, we will first examine the characteristics of those who are missing outcome data compared to those who are not, as well as those who were lost-to-follow-up and those who were not, to determine whether there are differences in important characteristics between the groups (e.g. age, race). To deal with missing data in the outcome, we will employ methodology such as the use of multiple imputation.

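### Section C's figure of 59 patients for 80% power does not hold at a 5% level: the z-test has an 11.8% false-positive rate there, and an exact 5% test needs 110

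*Combined protocol and SAP*

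**What the plan says.** Section C (Sample Size Considerations) sets a null hypothesis of an AF frequency of at most 1% against the one-sided alternative that it exceeds 1%, and says that "the z-test will assess the following hypotheses". For a true frequency of 5% it claims 97% power with 200 patients, meaning the chance that the null hypothesis "will be rejected at a significance level of 5% in favor of the alternate hypothesis". It then adds: "The sample size needed for 80% power is 59 patients". The 5% level appears in the explanation of the 200-patient figure; nothing suggests that a different level applies to the 59.

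The Methods section fixes enrolment: "The target sample size is 200 patients". Section C justifies going above 59 by a more precise estimate and a more useful analysis of AF predictors. It does not mention an exact test, a continuity correction, or the true error rate of the z-test at either sample size.

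**The concern.** A z-test for a proportion relies on the count of events being roughly normal. With a null frequency of 1%, the expected count under the null hypothesis is 59 × 0.01 = 0.59 at 59 patients and 200 × 0.01 = 2 at 200. Counts this small are discrete and strongly skewed, so a nominal 5% cutoff can have a quite different true error rate. A minimum sample size derived this way may be much too low.

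The figure matters because it tells the reader how much room the study has. Set against 59, a target of 200 is more than three times what the test requires (200 / 59 = 3.4), so a recruitment shortfall would appear to leave the hypothesis test intact. The z-test is also named as the analysis itself, so the problem would carry into the result and would be worst in a small achieved sample.

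**Working it through.** **Inputs, all from Section C:** null frequency p0 = 0.01; assumed true frequency p1 = 0.05; one-sided level 0.05 (critical value 1.645); sample sizes 59 and 200. The z-test variant is not stated. The one that reproduces both quoted figures uses the null variance without a continuity correction: z = (x/n − p0) / √(p0(1 − p0)/n), where x is the number of AF cases. Error rates and power below are exact binomial probabilities.

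**1. Reproducing the 59.** The standard error at n = 59 is √(0.0099/59) = 0.01295.
- x = 1: z = (0.01695 − 0.01)/0.01295 = 0.54, do not reject.
- x = 2: z = (0.03390 − 0.01)/0.01295 = 1.845, reject.

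The test rejects at 2 or more cases. Power at 5% is 1 − 0.95^59 − 59 × 0.05 × 0.95^58 = 1 − 0.0485 − 0.1506 = 0.801. At n = 58 it is 0.793, so 59 is the first size to pass 80%.

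**2. True error rate of that test.** At p = 1%: 1 − 0.99^59 − 59 × 0.01 × 0.99^58 = 1 − 0.5527 − 0.3294 = 0.118, against a stated 0.05.

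**3. Holding 5% at n = 59.** The cutoff must rise to 3, which removes the probability of exactly 2 cases (0.0965 at p = 1%, 0.2298 at p = 5%).
- Error rate: 0.1179 − 0.0965 = 0.021.
- Power: 0.8009 − 0.2298 = 0.571.

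**4. Stability of 59 under the plan's own test.** The z-test has at least 80% power for n = 59 to 66. At n = 67 the cutoff moves to 3 and power drops to 65.7%. It stays below 80% up to n = 84. So 59 is a product of the jumps in the cutoff. The usual normal-approximation formula does not give it either: [(1.645 × √0.0099 + 0.842 × √0.0475)/0.04]² = [(0.1637 + 0.1835)/0.04]² = 75.3, that is 76.

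**5. Sample size for a test that holds its level.** For the one-sided exact binomial test, take the smallest cutoff c with P(X ≥ c | 1%) ≤ 0.05, then compute P(X ≥ c | 5%).

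| n | Test | Reject at | True error rate | Power at 5% |
|---|---|---|---|---|
| 59 | z | ≥ 2 | 11.8% | 80.1% |
| 59 | exact | ≥ 3 | 2.1% | 57.1% |
| 100 | exact | ≥ 4 | 1.8% | 74.2% |
| 109 | exact | ≥ 4 | 2.4% | 79.98% |
| 110 | exact | ≥ 4 | 2.5% | 80.6% |
| 198 | z or exact | ≥ 5 | 5.0% (just under) | 97.2% |
| 200 | z | ≥ 5 | 5.17% | 97.4% |
| 200 | exact | ≥ 6 | 1.6% | 93.8% |

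The exact test first reaches 80% power at 110 and keeps it at every n from there to 399, the largest checked.

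**The case against.** The strongest reply is that 59 is neither a miscalculation nor an operative number. It follows correctly from the named test at its nominal level, as does the 97% at 200. The protocol mentions 59 only to explain why more patients are enrolled, and no rule allows stopping there. All of this is true. It limits the consequence but does not make the sentence correct, because at 59 patients the plan can have 80% power or a 5% error rate, not both.

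Second, the excess at 200 is trivial: 5.17% against 5%. Section F expects fewer than 2% to drop out. With 196 to 198 evaluable patients the z-test and the exact test share the cutoff of 5 and have about 97% power. This stands. The 94% figure and the cutoff of 6 apply only at 199 or 200 evaluable, and any restatement should say so.

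Third, 110 belongs to one particular test. A randomised test that uses the full 5% would reach 80% at about 95, and a mid-P test at 85. Neither rescues 59: the randomised test has 64% power there and is rarely used, while the mid-P test at 85 has a true error rate of 5.4%.

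Finally, the decision on a larger study rests on an observed frequency of about 5%, that is 10 or 11 of 200, which exceeds both cutoffs. The choice between 5 and 6 cannot change that decision at full enrolment. This is also correct.

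**Conclusion.** The concern holds. The 59-patient figure is wrong as a statement of 80% power at a 5% level: the true error rate of the z-test at that size is 11.8%, and a non-randomised test that holds 5% has 57% power. The required number is 110, nearly twice what is stated (110 / 59 = 1.9). This rests on the plan's own 1% and 5% frequencies, a one-sided 5% level, and a non-randomised exact binomial test.

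The target of 200 is not undermined. The practical error is in the apparent safety margin. The target is 1.8 times the minimum (200 / 110), not 3.4 times, and a study that ended with 60 or 100 patients would have 58% or 74% power with the exact test. At 200 the z-test's excess over 5% is negligible.

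**What to change.** In Section C, replace the z-test by the one-sided exact binomial test at the 5% level, reported with the matching one-sided 95% Clopper-Pearson lower bound. Let the cutoff follow from the number of evaluable patients: 6 or more AF cases at 199 or 200, and 5 or more at 196 to 198.

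Restate the two figures: power against a true frequency of 5% is about 94% with all 200 evaluable (about 97% with 196 to 198), and 110 patients are needed for 80% power at a true one-sided level of at most 5%. The argument that 200 gives better precision and a better predictor analysis can stay.

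The cost is wording only. The stated power at exactly 200 falls by three to four points and 59 becomes 110. Enrolment, procedures and follow-up do not change.
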